3.3.4.1 Withdrawal from trial treatment

An individual patient is to be withdrawn from trial treatment if:

- The patient wants to withdraw from trial treatment, without the need to justify the decision.
- The patient needs to take concomitant drugs that interfere with the investigational product. Refer to Section [4.2.2.2](#) for permitted and prohibited concomitant medications.
- The patient can no longer be treated with trial medication for other medical reasons (such as surgery, AEs, other diseases, or pregnancy). Refer to Section [4.1.4](#) for AEs that require treatment discontinuation.

Proprietary confidential information © 2021 Boehringer Ingelheim International GmbH or one or more of its affiliated companies

- The patient has repeatedly shown to be non-compliant with important trial procedures and, in the opinion of both, the investigator and sponsor representative, is not willing or able to stick to the trial requirements in the future.
- The patient experiences unequivocal PD by RECIST v1.1 and/or iRECIST.
- The patient completes 1 year of treatment. If the patient is benefiting clinically at 1 year, he/she may continue after a case-by-case review with the sponsor.

Given the patient's agreement, the patient will undergo the procedures for the end-of-treatment (EOT) visit and follow up as outlined in the [Flow Chart](#) and Section [6.2.3](#). For all patients the reason for withdrawal from trial treatment (e.g. AEs) must be recorded in the CRF. These data will be included in the trial database and reported.

During the dose finding part, patients withdrawn for a reason other than having a DLT or patients who miss more than one visit during MTD evaluation period may be replaced after discussion in the SMC if the information that needed to be collected during that visit is not available and makes the patient non-evaluable for the PK analyses or safety parameters (including evaluation for DLTs).

Patients who come off trial due to a DLT will not be replaced.

If a patient should become pregnant during the trial, the treatment with BI 754091 and BI 754111 must immediately be stopped. The patient will be followed up until delivery or termination of pregnancy (see Section [5.2.7.9](#) for information on pregnancy forms). The data of the patient will be collected and reported in the eCRF until the last patient's last visit and any events occurring thereafter will be reported in the BI drug safety database.

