5. ASSESSMENTS

5.1 ASSESSMENT OF EFFICACY

5.1.1 Tumour assessments

The tumour response will be evaluated according to RECIST Version 1.1 ([R09-0262](#)) and iRECIST ([R17-0923](#)). The overview of iRECIST will be found in Appendix [10.6](#).

The assessment by the Investigator and/or the local radiologist will be the basis for continuation or discontinuation of the trial in an individual patient (in addition to safety). The baseline imaging must have been performed within 4 weeks prior to treatment with the trial medication and the Investigator will record the target and non-target lesions in the eCRF. The same method of assessment and the same technique must be used to characterise each reported lesion at baseline and during treatment. Lesions in previously irradiated areas may not be used as target lesions. Tumour assessments will be performed at screening (as close as possible to the treatment start and no more than 28 days before the start of study treatment), every 2 cycles (6 weeks \pm 5 days) for the first 6 months, then every 3 cycles (9 weeks \pm 5 days) thereafter, and at the EOT visit (if not performed within the previous 4 weeks).

If a patient discontinues trial medication for a reason other than PD, the tumour assessment according to RECIST and iRECIST will be performed according to standard of care until the last follow-up needed according to the protocol (PD, death, lost to follow-up, end of the trial).

Patients will be allowed to stay on treatment in the case of initial radiological PD, if the Investigator feels that it is in the patient's best interest, and the patient provides an additional consent. If a patient is considered to be confirmed progressive disease according to iRECIST (iCPD), the patient may still continue to receive treatment if the Investigator and sponsor agree that the patient is deriving clinical benefit, and the patient provides an additional consent.

Copies of CT/MRI/PET scan data will be collected by the sponsor for later radiomics assessment. It is planned to explore the potential for enhanced and improved baseline and on-treatment markers/ patterns of early efficacy based on comprehensive quantitative CT metrics, i.e. radiomics features, assessed in standard-of-care medical imaging data.

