5.6 APPROPRIATENESS OF MEASUREMENTS

All assessments except for iRECIST have been planned in accordance with traditional oncology Phase I trial methodology.

iRECIST is a new guideline for response assessment and still to be validated, so this guideline will be used as an exploratory efficacy assessment in this trial.

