In scenario 2 (Low-toxicity scenario), almost all simulated trials (93.8%) are declared as MTD in underdose or target dose. The result is similar to scenario 1.

In scenario 3 (High-toxicity scenario), 75.4 % of the simulated trials are declared to MTD with true toxicity rate in the target intervals. Though overdose toxicity is assumed but the only 1.5% is declared as MTD in overdose.

In scenario 4 (Low-High scenario) shows 66.9% of the simulated trials declared a dose as MTD with true DLT rate in the targeted dose range. 18.2% of the simulated trials declared a dose as MTD in the overdose range. This is because the assumed true dose-toxicity rate at 240/600 mg and 240/800 mg was above 33%.

The mean patients numbers range is from 3 to 60 patients and the DLT numbers range is from 0 to 9.

In summary, the considered data scenarios show a reasonable behaviour of the model and the operating characteristics demonstrate a good precision of MTD determination.

10.6 iRECIST

Immunotherapeutics may result in infiltration of immune cells leading to transient increase in the size in malignant lesions, or undetectable lesions becoming detectable. The criteria are identical to those of RECIST 1.1 in many respects but have been adapted to account for instances where an increase in tumour burden, or the appearance of new lesions, does not reflect true tumour progression. Key differences are described below. All responses defined using iRECIST criteria are designated with a prefix. iRECIST time-point and best overall responses will be recorded separately.

Confirming progression

Unlike RECIST 1.1, iRECIST requires the confirmation of progression and uses the terms iUPD (unconfirmed progression) and iCPD (confirmed progression). Confirmatory scans should be performed at least 4 weeks, but no longer than 8 weeks after iUPD.

iCPD is confirmed if further increase in tumour burden, compared to the last assessment, is seen as evidenced by one or more of the following:

- Continued increase in tumour burden (from iUPD) where RECIST 1.1 definitions of progression had been met (from nadir) in target, non-target disease or new lesions
 - Progression in target disease worsens with an increase of at least 5 mm in the absolute value of the sum
 - Continued unequivocal progression in non-target disease with an increase in tumour burden

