 - Increase in size of previously identified new lesion(s) (an increase of at least 5 mm in the absolute value of the sum of those considered to be target new lesions) or additional new lesions
- RECIST 1.1 criteria are met in lesions types (target or non-target or new lesions) where progression was not previously identified, including the appearance of additional new lesions.

If iUPD is not confirmed at the next assessment, then the appropriate response will be assigned (iUPD if the criteria are still met, but no worsening, or iSD, iPR or iCR if those criteria are met compared to baseline). The prior documentation of iUPD does not preclude assigning iCR, iPR, or iSD in subsequent time-point assessments or as best overall response (BOR) providing that iCPD is not documented at the next assessment after iUPD.

New lesions

New lesions should be assessed and measured as they appear using RECIST 1.1 criteria (maximum of 5 lesions, no more than 2 per site, at least 10 mm in long axis (or 15 mm in short axis for nodal lesions), and recorded as New Lesions-Target (NLT) and New

Proprietary confidential information © 2021 Boehringer Ingelheim International GmbH or one or more of its affiliated companies

Lesion-Non-Target (NLNT) to allow clear differentiation from baseline target and non-target lesions.

New lesions may either meet the criteria of NLT or NLNT to drive iUPD (or iCPD). However, the measurements of target lesions should NOT be included in the sum of measures of original target lesions identified at baseline. Rather, these measurements will be collected on a separate table in the case record form.

PD is confirmed in the New Lesion category if the next imaging assessment, conducted at least 4 weeks (but not more than 8 weeks) after iUPD confirms further progression from iUPD with either an increase of at least 5 mm in the absolute value of the sum of NLT OR an increase (but not necessarily unequivocal increase) in the size of NLNT lesions OR the appearance of additional new lesions

Table 10.6: 1 Time-point (TP) iResponse

Target Lesions*	Non-Target Lesions*	New Lesions *	Time Point Response	
			No prior iUPD**	Prior iUPD**; ***
iCR	iCR	No	iCR	iCR
iCR	Non-iCR/Non-iU PD	No	iPR	iPR
iPR	Non-iCR/Non-iU PD	No	iPR	iPR
iSD	Non-iCR/Non-iU PD	No	iSD	iSD

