7.4 PRIMARY ENDPOINT(S)

Maximum tolerated dose (MTD) of ezabenlimab (Part I) and ezabenlimab plus BI 754111 combination (Part II);

Number of patients experiencing Dose Limiting Toxicities (DLTs) during the MTD evaluation period in patients with solid tumours

In order to identify the MTD and the recommended dose for ezabenlimab (Part I) and ezabenlimab in combination with BI 754111 (Part II), the number of patients with DLTs at each dose level during Part I and Part II (first three weeks) must be presented. Patients who discontinue during the first treatment course for reasons other than a DLT will be excluded from the determination of the MTD.

The analysis of the MTD is based on a BLRM guided by the escalation with overdose control principle. The MTD is defined as the highest dose for a given schedule that is expected to cause less than 25% risk of the true DLT rate being above or equal to 33% during the MTD evaluation period. Estimation of the MTD during the dose escalation phase of the study will be based upon the estimation of the posterior probability of the incidence of DLT in toxicity categories during the MTD evaluation period for all evaluable patients. The model to be used is specified in CTP Section 7.

In addition, the number of patients with DLTs that occurred during the trial will be summarised at each dose level (Part I and Part II) and each cohort (Part III). The BLRM will be rerun to re-evaluate the MTD and RD together with all relevant data collected during Part III.

Objective response (OR) - confirmed complete response (CR) and partial response (PR) according to RECIST Version 1.1 as assessed by the Investigator

For Part III, OR according to RECIST Version 1.1 will be summarised descriptively with exact 95% Clopper-Pearson CIs. Response data collected after the EOT or the start of subsequent anti-cancer therapy will not be used. This applies to other endpoints based on the response data. Confirmed best overall response (BOR) will be derived according to the following derivation rules:

- If CR or PR: look at subsequent visits, if there is another CR or PR ≥ 28 days and no more than one missing visit (defined by time window [Table 6.7: 1](#)) in between, then the patient has a confirmed response. If there is not another CR or PR ≥ 28 days and / or more than one missing visit between the two responses, then the patient can be a confirmed SD if the CR or PR is ≥ 39 days from start of combination therapy.

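### The best-response rule in SAP 7.4 has no cut-off at first RECIST 1.1 progression, so post-progression responses can enter the primary ORR; its 39-day SD limit and PR-then-SD row can also misclassify disease control

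*SAP*

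**What the plan says.** **Endpoint.** The Part III primary endpoint is confirmed CR or PR by RECIST 1.1, investigator-assessed (Protocol 2.1.2, SAP 5.1).

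**Derivation.** SAP 7.4 sets one limit on the data: "Response data collected after the EOT or the start of subsequent anti-cancer therapy will not be used". This also applies to the other response-based endpoints. Its first bullet reads "If CR or PR: look at subsequent visits, if there is another CR or PR" at least 28 days later, with no more than one missed visit between, and then calls the response confirmed. An earlier or intervening PD is not mentioned. None of the nine rows of Table 7.4:1 starts with PD.

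**Treatment after progression.** Protocol 3.3.4.1 lists as a reason to withdraw from treatment: "The patient experiences unequivocal PD by RECIST v1.1 and/or iRECIST". Protocol 5.1.1 says: "Patients will be allowed to stay on treatment in the case of initial radiological PD", subject to investigator judgement and extra consent. After confirmed iRECIST progression it adds that "the patient may still continue to receive treatment if the Investigator and sponsor agree that the patient is deriving clinical benefit".

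**Role of iRECIST.** Protocol 5.6 states that "this guideline will be used as an exploratory efficacy assessment in this trial". Appendix 10.6 presents response after unconfirmed progression as an iRECIST feature: "The prior documentation of iUPD does not preclude assigning iCR, iPR, or iSD in subsequent time-point assessments". It also says "iRECIST time-point and best overall responses will be recorded separately".

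**Stable disease.** SD needs one reading at 39 days or more from the start of combination therapy. If a PR is followed by SD, the table gives SD when the 39 days are met and PD otherwise. DCR counts a best response of CR, PR or SD (SAP 7.5.2.2).

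**The concern.** There are two separate faults.

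**(a) No cut-off at PD (ORR and DCR).** For a patient who stops at PD, EOT does the work of a PD cut-off. For a patient treated beyond PD it does not. Scans continue, and the rule as written lets later responses count under a RECIST 1.1 label. By the SD bullet, PD followed by a single SD reading also counts as disease control. The ORR is judged against the thresholds in Protocol Table 7.7.2:1, which were set with historical ORRs in mind, and it feeds the futility look if one is held. For PD-PR-PR the duration of response has no meaning, because the PD comes before the response.

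**(b) SD limit and PR-then-SD row (DCR only).** An on-time first scan can fall before day 39. The PR-then-SD row can also assign PD to a patient with no recorded PD.

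**Working it through.** **1. The rule applied to sequences (days from start)**

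| Sequence | First bullet, literally | Table 7.4:1 | Data cut at first PD |
|---|---|---|---|
| PD 42, PR 84, PR 126 | confirmed PR | no PD-first row | not a responder |
| PR 42, PD 84, PR 126 | confirmed PR | SD (PR-then-PD row) | not a responder |
| SD 42, PD 84, PR 126, PR 168 | confirmed PR | no row covers the PD | not a responder |

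In each case the two PRs are at least 28 days apart and no visit is missed. In the second sequence the bullet and the table contradict each other.

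**2. Reproducing the plan's two-stage figures**

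Inputs from Protocol 7.7.2: stage 1 n = 17, total n = 35. Cohort A stops below s = 3 and aims for r = 9. Cohort D stops below s = 2 and aims for r = 7.

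- P(stop) = P(X1 ≤ s−1), with X1 ~ Bin(17, p).
- P(reach) = Σ over x ≥ s of P(X1 = x) · P(X2 ≥ r−x), with X2 ~ Bin(18, p).

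Cohort A at p = 0.10: P(stop) = 0.9^17 + 17(0.1)(0.9^16) + 136(0.01)(0.9^15) = 0.1668 + 0.3150 + 0.2800 = 0.762.

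| Cohort, true ORR | Plan: stop / reach | Recomputed |
|---|---|---|
| A, 10% | 77% / 1% | 76.2% / 0.6% |
| A, 35% | 3% / 90% | 3.3% / 89.8% |
| D, 5% | 80% / 0% | 79.2% / 0.1% |

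All 25 rows for Cohorts A to D agree within 2 points, so the table itself is sound.

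**3. Effect of counting post-PD responses**

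The documents give no rate, so 0, 2 and 5 added points are assumptions.

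| Cohort, true ORR | Added points | Early stop | Reach final threshold |
|---|---|---|---|
| A, 10% | 0 / 2 / 5 | 76.2% / 66.5% / 52.0% | 0.6% / 1.9% / 6.5% |
| D, 5% | 0 / 2 / 5 | 79.2% / 66.4% / 48.2% | 0.1% / 0.9% / 5.3% |

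One patient adds 1/35 = 2.9 points at the end. For example, 8/35 = 22.9% (95% CI 10.4 to 40.1) becomes 9/35 = 25.7% (12.5 to 43.3), which crosses Cohort A's 25% mark. At the futility look one patient adds 1/17 = 5.9 points; 2/17 stops Cohort A and 3/17 does not. The early-stop figures assume the post-PD response is already confirmed at the look. PD at week 6 with PR at weeks 12 and 18 is just complete at the third scan.

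**4. The 39-day limit**

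The first scan is due at 6 weeks ±5 days (Flow Chart footnote m).

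- Counting elapsed days: 42±5 = 37 to 47, so 2 of 11 permitted days (37 and 38) fail the limit.
- Counting as in SAP Table 6.7:1, where first dose is Day 1 and the scan is due on Day 43: 38 to 48, so 1 of 11 (Day 38) fails.

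SAP 7.4 does not say which count applies. These are shares of permitted days, not misclassification rates.

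An SD on elapsed day 37 or 38 with nothing evaluable afterwards becomes NE. If PD follows, no row covers it and PD is the natural result.

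**5. The PR-then-SD row**

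Take PR on day 38, SD on day 80 and no PD ever seen. The row gives PD, so no disease control. The SD bullet gives SD, so disease control. The same conflict arises for an earlier unscheduled PR scan, which footnote m allows.

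**The case against.** The best reply to (a) is that the RECIST 1.1 label already ends response assessment at PD. Appendix 10.6 treats response after progression as a departure from RECIST 1.1, Table 7.4:1 downgrades CR-then-PD and PR-then-PD to SD, and duration of response runs from response to PD. That probably shows the intent. It does not change the operative rule: the bullet ignores PD, the only data limits named are EOT and new therapy, and for PR-PD-PR the bullet and the table disagree.

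Several limits do stand:

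- The affected group may be small. Staying on after PD needs investigator judgement and extra consent, and the patient must then show two responses before EOT.
- The size is assumed. The 5-point case doubles Cohort D's 5% rate, and at 0 points nothing changes.
- The futility look is held only if deemed appropriate, the visible SAP does not say that it uses this derivation, and no formal test or formal comparison with historical rates is planned.
- Parts of the SAP are withheld. The visible 7.4 text reads as continuous, but a PD cut-off stated in withheld text would answer (a).

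On (b), a minimum SD duration is a design choice and need not equal the earliest permitted scan. Still, a limit that fails on-time scans needs a reason, and none is given. One could also read the row's 39 days as referring to the SD reading; because that reading comes at least 28 days later, the PD branch would then need a PR before day 39 − 28 = 11. However, the first bullet ties the 39 days to the date of the CR or PR.

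**Conclusion.** Both parts hold.

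(a) As written, SAP 7.4 counts some post-progression responses in the primary RECIST 1.1 ORR and contradicts its own table for PR-PD-PR. This is confined to patients treated beyond PD. Each PD-PR-PR patient is worth 2.9 points at 35 patients and 5.9 points at 17; any larger effect rests on the assumed rates.

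(b) The 39-day limit and the PR-then-SD row can each move a patient out of disease control, at 2.9 points per patient. This needs a scan on one or two particular days, or an unscheduled early scan. For SD it also needs no later qualifying reading. It cannot change ORR.

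In DCR, (a) pushes up and (b) pushes down, so the net direction is not established. With no formal test, the consequence is for the reported estimates and the go/stop reading, not for a type I error claim. It should be fixed.

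**What to change.** In SAP 7.4:

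1. Derive best overall response from RECIST 1.1 assessments up to and including the first RECIST 1.1 PD, EOT or start of subsequent therapy, whichever comes first. Require no PD before or between the two responses. Add PD-first rows to Table 7.4:1. Report later responses under iRECIST only.
2. Set the SD minimum to 37 elapsed days (42 − 5) to match the current window, and state how days are counted.
3. Make the PR-then-SD row give SD when the SD reading meets the limit, and never PD without a recorded PD.

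The cost is a few lines of text and programming, with no new data. The reported ORR may be slightly less favourable.

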7.5 SECONDARY ENDPOINT(S)

7.5.1 Key secondary endpoint

This section is not applicable as no key secondary endpoint has been defined in protocol.

7.5.2 Other secondary endpoints

7.5.2.1 Other secondary endpoints in Part I and Part II

PK parameters evaluated after the single and after multiple administrations of ezabenlimab in combination with BI 754111, and also for ezabenlimab after single and multiple doses of therapy

The PK parameters will be evaluated using noncompartmental analysis methods according to 001-MCS-36-472_RD1 [2].

Descriptive statistics will be calculated for all concentration time points and PK parameters. The following descriptive statistics will be calculated for ezabenlimab and BI 754111 concentrations: N (number of patients with non-missing values), arithmetic mean, standard deviation, minimum, median, maximum, arithmetic coefficient of variation, geometric mean, and geometric coefficient of variation and for PK parameters: N, arithmetic mean, standard deviation, minimum, median, maximum, tenth percentile (P10), Q1, Q3, ninetieth percentile (P90), arithmetic coefficient of variation, geometric mean, and geometric coefficient of variation.

Treated and evaluable patients will be included in the PK analysis. A patient is considered not evaluable if the patient had an important protocol violation relevant to the evaluation of PK or had insufficient PK data. Non evaluable patients will be listed with their individual PK parameters, but such data will not be included when calculating descriptive statistics. If the data suggest a PK / PD relationship of special parameters (e.g. PK vs. RO), a detailed analysis may be performed and documented in a separate report.

OR for patients with solid tumors according to RECIST Version 1.1 as assessed by the investigator

OR will be summarized descriptively with exact 95% Clopper-Pearson CIs. Derivation rule of confirmed BOR is defined in [Table 7.4:1](#).

7.5.2.2 Other secondary endpoints in Part III

Duration of response according to RECIST Version 1.1 as assessed by the Investigator

Duration of response is defined as the duration from the date of first documented PR or CR according to RECIST Version 1.1 as assessed by the Investigator to the date of PD or death. Duration of response will be summarized descriptively by quartiles with 95% confidence interval (based on the Greenwood's method) calculated from Kaplan-Meier estimate. Kaplan-Meier plots will also be produced. Duration of objective response will use the censoring rule defined in below Table 7.5.2.2:1

[figure not shown]
Table 7.5.2.2:1 Censoring rules and determination of date of event or censoring for duration of response

[figure not shown]
Situation	Outcome (event or censored)	Date of outcome
No other anti-cancer therapy		
Alive and not progressed, no missed radiological assessments window*	Censored	Date of last radiological assessment
Alive and not progressed, one or more consecutively missed radiological assessments window*	Censored	Date of last radiological assessment prior to missed radiological assessments
Progressed, no radiological assessment window* prior to progression	Event	Date of radiological assessment of progression
Progressed, but one or more consecutively missed radiological assessments window* prior to progression	Censored	Date of last radiological assessment prior to missed radiological assessments
Death but no progression, no missed radiological assessment window* prior to death	Event	Date of death
Death without progression, but one or more consecutively missed radiological assessments window* prior to death	Censored	Date of last radiological assessment prior to missed radiological assessments
Initiation of subsequent anti-cancer therapy		
Subsequent anti-cancer therapy started before progression or death, no missed radiological assessments window* prior to start of subsequent anti-cancer therapy	Censored	Date of last radiological assessment before initiation of subsequent anti-cancer therapy

[figure not shown]
* Windows for radiological assessments are defined in [Table 6.7: 1](#)

[figure not shown]
Disease control according to RECIST Version 1.1 as assessed by the Investigator

Disease control is defined as a BOR of CR, PR or SD. Disease control rates will be presented with exact 95% Clopper-Pearson CIs.

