7.3.2.2 Secondary endpoint analyses for Part III

Duration of response – for all patients with an OR, the duration of OR will be calculated as follows:

For patients with PD or death:

- Duration of response [days] = date of outcome – date of first assessment indicating OR + 1

For patients without disease progression or death:

- Duration of response (censored) [days] = date of outcome – date of first assessment indicating OR + 1

The censoring rules for OR (i.e., outcome and date of outcome) are described in the TSAP.

The outcome will be assessed according to RECIST 1.1.

Kaplan-Meier estimates will be used to calculate median duration of OR.

Disease control (DC) will be analysed in terms of DC rate (DCR), defined as the proportion of patients with best overall response of CR, PR, or SD according to RECIST 1.1.

Proportions will be presented with 95% two-sided confidence interval using the exact Clopper-Pearson method.

[7.3.5](#)

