6.7 BASELINE, TIME WINDOWS AND CALCULATED VISITS

Baseline values will be the measurements taken most recently prior to first administration of study drug.

For the laboratories not only the examination date but also time is recorded, examination time has to be taken into account when defining baseline. That is, a laboratory value on the same date as the first study drug administration is considered as baseline value if and only if the time of laboratory value is before or the same as the time of study drug administration. If any of these times is missing and the date of laboratory assessment is equal to the date of first drug administration, then the laboratory assessment will be considered as according to protocol, i.e. as prior to first study medication.

Study day will be calculated relative to the date of the first administration of study drug. The day prior to first administration of study drug will be “Day -1” and the day of first administration of study drug will be “Day 1”; therefore “Day 0” will not exist.

[figure not shown]
In order to identify whether consecutive imaging time points are missing for a given patient, a nominal time point (i.e. Week 6, 12, 18 ... etc.) will be assigned to each and every image. This is achieved by creating windows for every radiological response assessment. These windows are defined in Table 6.7: 1.

Table 6.7: 1 Nominal time points and windows for imaging

Nominal time point (weeks from start of study medication)	Due date of scans (days)*	Window (days)
6	43	1 to \leq 64
12	85	65 to \leq 106
18	127	107 to \leq 148
24	169	149 to \leq 200
33	232	201 to \leq 263
42	295	264 to \leq 326
51	358	327 to \leq 389
9 week interval

* The date of the first dose of study medication is Day 1

If a patient does not have an image in one of the windows described above, the patient will be said to have missed an assessment for that time point.

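### Duration of response is censored after one empty scan window, although the same single gap is accepted when the response is confirmed

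*SAP*

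**What the plan says.** Protocol 7.3.2.2 measures DoR as the outcome date minus the "date of first assessment indicating OR + 1" and leaves the censoring rules to the SAP, so SAP Table 7.5.2.2:1 governs. Three of its rows censor at the last scan before the gap once a single window is missed:

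- "Alive and not progressed, one or more consecutively missed radiological assessments window"
- "Progressed, but one or more consecutively missed radiological assessments window* prior to progression"
- "Death without progression, but one or more consecutively missed radiological assessments window* prior to death"

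The row that counts progression as an event is worded "Progressed, no radiological assessment window* prior to progression". The word *missed* is absent there, although the parallel death row has it. No row restricts the gap to windows after the first response.

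SAP 7.4 confirms a CR or PR if a second one follows at least 28 days later with "no more than one missing visit" in between, judged on the same Table 6.7:1 windows. Those windows are calendar days from first dose. SAP 6.7 gives their purpose: "In order to identify whether consecutive imaging time points are missing for a given patient".

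Protocol 4.1.4 allows a dose to be delayed by up to 6 weeks for adverse events. Flow Chart footnote m moves the scan to the end of the delayed second or third cycle.

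**The concern.** One empty window is harmless when the SAP decides whether a patient responded, yet it ends observation when the SAP asks how long the response lasted. The scan that confirmed the response can itself fall after the DoR censoring date, and any later progression, death or continued response is then discarded. If one window is enough, the word *consecutively* in the table has no function, and the rule fits poorly with the purpose stated in SAP 6.7.

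Because the windows ignore cycle delays, a patient can be censored with no protocol scan missed. The permitted delays are for adverse events, so this route ties censoring to tolerability and the censoring may be informative. DoR is estimated in responders only. The final response targets in Protocol Table 7.7.2:1 correspond to 7 to 14 responders per cohort of 35 in Cohorts A to D, so a few lost events matter to Kaplan-Meier quartiles.

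**Working it through.** **1. The SAP's windows.** Due day = 7 × week + 1, giving 43, 85, 127, 169, 232, 295 and 358. Upper limit = midpoint of adjacent due days, rounded down, for example (43 + 85)/2 = 64 and (169 + 232)/2 = 200.5 → 200. This gives 64, 106, 148, 200, 263, 326 and 389. All 14 values match Table 6.7:1. With no delay, and with every scan 5 days early or late, no window is empty.

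**2. A skipped scan.** PR on Day 43, nothing in Days 65-106, PR on Day 127. The interval is 127 − 43 = 84 days (at least 28) with one missing visit, so the response is confirmed. Under the DoR table the outcome date is Day 43: 43 − 43 + 1 = **1 day, censored**.

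**3. A permitted delay.** A window empties once the delayed scan passes its upper limit:

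- Week 12: 85 + 22 = 107 > 106. The same 22 days applies at Weeks 6 and 18. With the ±5-day scan tolerance the threshold is 17 to 27 days.
- Week 24: 169 + 32 = 201 > 200. The same 32 days applies at Weeks 33, 42 and 51.

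Both lie inside the 42 days allowed. Example: first PR on Day 85, cycle 5 delayed by 42 days. The Day 127 scan moves to Day 169, leaving Days 107-148 empty, and the next scan is on Day 211. If Day 169 shows PR and Day 211 shows progression, the table censors at 85 − 85 + 1 = 1 day. Tolerating one gap gives an event at 211 − 85 + 1 = **127 days**.

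A single delay of 0 to 42 days placed before each scheduled scan in turn never emptied two consecutive windows. Two delays can add up: 11 days before cycle 3 and again before cycle 5 move the Day 127 scan to Day 149, past the limit of 148.

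**4. Gaps before response.** If the Week 6 window is empty and first PR is on Day 85, the last scan before the gap is the screening scan. Read literally, the censoring date precedes the start of the response.

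**5. How many responders.** The documents give no miss rate. Assume a rate *p* per window, random and independent, over *n* windows after first response.

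- Present rule: 1 − (1 − p)^n; for p = 5% and n = 5, 1 − 0.95^5 = 22.6%.
- Two consecutive misses: start with a = 1, b = 0. For each window replace (a, b) by ((a + b)(1 − p), a·p). The probability is 1 − (a + b) after *n* windows.

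| p | Present rule, n = 3 / 5 / 6 | Two consecutive, n = 3 / 5 / 6 |
|---|---|---|
| 2% | 5.9 / 9.6 / 11.4% | 0.08 / 0.16 / 0.20% |
| 5% | 14.3 / 22.6 / 26.5% | 0.5 / 0.96 / 1.2% |
| 10% | 27.1 / 41.0 / 46.9% | 1.9 / 3.7 / 4.6% |

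The extreme 1-day value needs the window directly after first response to be empty, which affects a share *p* of responders. Later gaps truncate later.

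**The case against.** The strongest reply is that *prior to progression* and *prior to death* may mean only the gap leading directly into the event, where the event time is uncertain. On that reading a patient whose scanning resumed before progression keeps the event, and the loss is about *p* rather than 1 − (1 − p)^n. The wording does not support it. The event row for death requires that no window was missed before death, and the first alive row requires no missed window at all. A patient with any earlier gap therefore falls into the censored rows.

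Other points stand in part:

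- Confirming a response and dating its end are different questions and need not share a tolerance. But the SAP gives no reason for the difference, and uncertainty about scan timing does not explain discarding a death whose date is exact.
- Only long delays trigger the rule: the windows absorb 21 days after the due date through Week 18 and 31 days from Week 24. A discretionary scan could also fill a window.
- Five windows presuppose long follow-up, such as first response at Week 6 followed to Week 42. SAP 7.4 also says "Response data collected after the EOT or the start of subsequent anti-cancer therapy will not be used", so early discontinuation means fewer windows. The three-window column covers shorter follow-up.
- Absolute numbers are small. At the favourable response rates of 30% to 45%, 35 patients yield 35 × 0.30 = 10.5 to 35 × 0.45 = 15.75 responders. At p = 5% and n = 5 about 2.4 to 3.6 are truncated (× 0.226), against 0.5 to 0.8 on the narrow reading (× 0.05).
- A censoring date before the response began is plainly unintended, so that part is a drafting defect.

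**Conclusion.** The concern holds and should be fixed. One empty window ends DoR follow-up, the same gap is accepted for confirmation in SAP 7.4, and a patient treated and scanned within the protocol can be caught by it. The established harm is loss of observed progressions, deaths and follow-up time in an endpoint estimated only in responders. The direction of any bias cannot be determined from the documents.

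The 1-day example and the 22- and 32-day thresholds follow from the documents alone. The percentages rest on assumed miss rates that are independent between windows, and on three to six windows of follow-up. They count truncated responders, not all of whom would have had a later event. The primary objective response and its futility rules are unaffected, and no formal test uses DoR.

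**What to change.** In SAP Table 7.5.2.2:1:

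1. Change the trigger from one to *two or more consecutively missed* windows in the alive, progression and death rows alike.
2. Make the complementary rows read *no more than one consecutively missed*, including the subsequent-therapy row and the progression row that now lacks *missed*.
3. State that only windows after the first documented response count.

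Leave Table 6.7:1 unchanged, because it also feeds the primary confirmed best overall response. The two-window rule already covers a single permitted delay; it would not cover every combination of long delays.

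If the sponsor keeps the strict rule, item 3 and the missing word still need correcting, and a sensitivity analysis should count progression or death after one missed window as an event.

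The cost is SAP wording and programming. The statistical price is a less precise progression date after one skipped scan, late by up to about one scan interval (6 or 9 weeks).
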